3.2.6 Patient Data Collection

The patient questionnaire will be self-administered (closed-ended questions with predefined answers) on hard copy forms at the site. While there are a number of advantages to using an electronic format for questionnaire administration, we anticipate a paper format will be

preferred in this case based on the study population (e.g., older patients). Written informed consent will be obtained from each patient prior to completion of this questionnaire.

Patients will be asked to complete the questionnaire in the physician's office in a private setting. Sites will provide patients with appropriate privacy so there is no influence by the physician (or patient perception thereof) in this process. Patients will be asked to complete the questionnaire without referring to the patient alert card. Once they have completed the questionnaire, the patient will be asked to review the patient alert card and then re-answer selected questions related to key safety information to gather data on patient knowledge immediately after exposure to the card. Patients will then place their completed forms in an envelope and give the sealed envelope to a study coordinator or designee. While participating physicians will be informed of the purpose of the study, they will be counselled not to alter routine practice and patient education so as not to influence the study results. Physicians will be advised that the ultimate goal of the study is to evaluate the educational materials.

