3.2.5 Patient Questionnaire Development

The patient questionnaire has also been developed following standard survey methodologic principles and has been cognitively tested with patients in each of the target countries. Modifications have been made to the questionnaire based on the results of testing and additional feedback from the sponsor. The final version of the questionnaire can be found in Appendix D. Some modifications to the questionnaire are anticipated based on country-specific requirements. The questionnaire will assess patient knowledge of the following concepts:

- Receipt and use of the patient alert card
- Knowledge of the key safety messages outlined in the patient alert card:
 - Signs or symptoms of bleeding and when to seek attention from a health care provider
 - Importance of treatment compliance
 - Necessity of taking the 15-mg and 20-mg tablets with food
 - Necessity of carrying the patient alert card at all times
 - Necessity of informing HCPs that they are taking rivaroxaban if they need to have surgery or invasive procedures

The questionnaire includes demographics and other patient information to help characterise patterns of knowledge and behaviour through stratification of results. The questionnaire has been designed to take approximately 20 minutes to complete.

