Appendix D.

Patient Questionnaire

**Xarelto Risk Minimization Study
Survey Instructions**

Thank you for agreeing to participate in this study!

Taking part in this study will take approximately 20 to 25 minutes of your time. Your responses will be kept completely confidential and will not be shared with your health care professionals (e.g., surgery or hospital based doctor or nurse).

This survey consists of two questionnaires. Please follow the instructions below to complete the survey. If you have any questions, please ask the study coordinator for help.

Step 1 - Open envelope #1 and complete the first questionnaire. Please do not refer to the Xarelto patient alert card or other Xarelto educational materials while answering the questionnaire.

Step 2 – When you have completed the first questionnaire, place it back into the envelope and seal the envelope.

Step 3 – Open envelope #2. Inside the envelope you will find a Xarelto patient alert card. Please read the Xarelto patient alert card. After you have read it, complete the second questionnaire.

Step 4 - When you have completed the second questionnaire, place it back into the envelope and seal the envelope.

Step 5 – Return both envelopes to the study coordinator.

**Xarelto Risk Minimization Study
Patient Questionnaire #1**

This is the first of two questionnaires. Please complete this questionnaire before moving on to the second questionnaire (found in a separate envelope).

Please answer the following questions first to confirm that you are eligible for this study.

S1. Are you 18 years of age or older?

- Yes
- No (If no, please speak with the study coordinator to confirm your eligibility.)

S2. Have you taken Xarelto (also known as rivaroxaban) in the past 3 months?

- Yes, I have taken Xarelto in the past 3 months
- No, I have not taken Xarelto in the past 3 months
- I don't know

The purpose of this study is to learn more about your knowledge and understanding of the safety information related to Xarelto (rivaroxaban).

Please do not look at the Xarelto patient alert card while answering the following questions.

Q1. Are you currently taking Xarelto?

- Yes
- No
- I don't know

Q2. Approximately how long have you been taking Xarelto?

Select the one answer that best applies to you.

- Less than 1 month
- Between 1 and 6 months
- More than 6 months but less than 1 year
- More than 1 year
- I don't know

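### Section 3.2.6 seals the patient forms only after the alert card has been read, whereas Appendix D seals questionnaire #1 before the card envelope is opened; the two need to be reconciled

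*Protocol*

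**What the plan says.** Section 3.2.6 (Patient Data Collection) sets out a paper procedure at the site. Before the card: "Patients will be asked to complete the questionnaire without referring to the patient alert card". After the questionnaire is finished, "the patient will be asked to review the patient alert card and then re-answer selected questions related to key safety information". The sealing step comes last: "Patients will then place their completed forms in an envelope and give the sealed envelope to a study coordinator or designee". The forms are plural, the envelope is singular, and nothing is sealed before the card is read.

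Appendix D has a different sequence, and Section 3.2.5 gives it standing: "The final version of the questionnaire can be found in Appendix D". Its survey instructions run in five steps:

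- Step 1, during questionnaire #1: patients are asked to consult neither the card nor any other material on the drug.
- Step 2, once it is finished: "When you have completed the first questionnaire, place it back into the envelope and seal the envelope".
- Step 3, on opening envelope #2: "Inside the envelope you will find a Xarelto patient alert card".
- Step 4: questionnaire #2 goes into its own envelope, which is sealed.
- Step 5: "Return both envelopes to the study coordinator".

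The instruction to seal is repeated at the end of questionnaire #1. The order of the two questionnaires is restated at the head of each.

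**The concern.** Questionnaire #1 measures what patients know unaided. Patient awareness and understanding are part of the primary objective (Section 2), so this is a main result of the patient assessment. It is also the baseline against which knowledge after reading the card is compared. If a patient can still write on the first form while reading the card, wrong or uncertain answers can be put right from the card, and the form no longer measures unaided knowledge.

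For an evaluation of risk-minimisation material the direction of the error matters. Existing knowledge would look better than it is, and the card would look less informative than it is. A larger sample does not reduce such an error. Edits of this kind may also be undetectable once the forms have been collected. The protocol cares about the same threat elsewhere: Section 3.1.6 stops physicians from returning to earlier answers.

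**Working it through.** No figure in the protocol is in dispute, so the check is a comparison of texts, followed by the direction of any bias.

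**1. The two sequences side by side**

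| Step | Section 3.2.6 | Appendix D |
|---|---|---|
| Number of envelopes | One | Two |
| State of the first form when the card is read | Not yet sealed | Sealed in envelope #1 |
| Where the study copy of the card is beforehand | Not stated | Inside envelope #2 |
| When the first form is handed in | At the end, with the other form | At the end, with envelope #2 |
| When the card is issued | After the questionnaire is completed; by whom is not stated | Not stated |

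Rows 1 and 2 contradict each other. Row 4 is common to both texts: neither has the first form collected before the card is read.

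**2. Which answers are exposed**

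Questions 1 to 9 of questionnaire #2 repeat questions 4 and 8 to 15 of questionnaire #1: nine questions covering the purpose of the drug, bleeding risk, signs of bleeding, stopping, other medication, surgery, reporting bleeding, food and adherence. The card in Appendix B addresses each of these. The exposed questions are therefore the ones used in the before/after comparison, and the card supplies the correct responses.

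**3. Direction of the bias if Section 3.2.6 is followed literally**

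Let p1 be the true unaided proportion correct on a question, p2 the proportion correct after the card, and d the proportion of all patients who change a wrong or don't-know answer on the first form to a right one because of the card. Then

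- observed pre-card proportion = p1 + d
- observed gain = p2 − (p1 + d) = (p2 − p1) − d

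Unaided knowledge is raised by d and the gain is lowered by the same d, whatever the sample size. The protocol gives no value for p1, p2 or d, so no size can be attached.

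**4. What remains under Appendix D**

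Editing form #1 after reading the card means reopening a sealed envelope, which is a real obstacle. Looking ahead is a different route. If envelope #2 is in the patient's hands during questionnaire #1, only the order of the steps and the request not to consult the card keep it closed. Whether the patient holds it at that point is not stated; that is an inference from Step 5, which returns both envelopes together.

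**5. Does the limitations text cover this?**

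Section 5 accepts that patients cannot be prevented from altering paper answers, but it ties this to what they learn while filling in the questionnaire. It does not mention changes made after reading the card, which sealing the form would largely prevent.

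**The case against.** The strongest reply is that patients work from the printed instructions, not from Section 3.2.6. The forms are self-administered, Appendix D is declared final, and it seals first and says so more than once. On this view Section 3.2.6 is a summary that omits the intermediate seal. It does not tell sites to leave the first form open, and nothing suggests that a site would discard the two-envelope pack. Much of this stands, and it makes the literal Section 3.2.6 scenario less likely. It does not remove the contradiction: the protocol body describes the weaker procedure, and Section 3.2.5 expects country-specific changes to the questionnaire, so the body text should carry the safeguard.

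A reader might go further and infer that the unaided answers have no protection under either text, or that the request not to look is all that stands in the way. The documents do not support that for Appendix D, where sealing form #1 and enclosing the card in envelope #2 are genuine barriers. Nor do they state that the patient holds envelope #2 while answering form #1.

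It is also fair to say that collecting envelope #1 early does not close every route. Participants already use the drug, and the card tells them to carry it at all times, so some may bring their own. That limits what the remedy can achieve, but it is no reason to leave the study copy uncontrolled.

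**Conclusion.** The point holds as an internal contradiction with a clear direction of risk. As written, Section 3.2.6 leaves the unaided answers open to correction from the card; Appendix D largely prevents this. Under Appendix D the remaining gap is narrower: the time at which envelope #2 is issued is not fixed, so opening it early is prevented only by instruction.

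The direction (pre-card knowledge too high, gain too low) rests on the assumption that any edits move answers towards what the card says. The size cannot be estimated from the protocol, and an assumed rate of look-ahead or revision would be a guess. It would also go too far to conclude that sites will in fact differ, or that results will not be comparable between sites or between the assessments at 18 months, 3 years and 7 years. That would require some sites to work from Section 3.2.6 instead of the printed instructions, and nothing in the document shows this. The point is an inexpensive improvement worth making before fielding.

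**What to change.** 1. In Section 3.2.6, replace the single-envelope sentence with the two-envelope sequence: questionnaire #1 is completed and sealed, the coordinator or designee collects it, envelope #2 with the card and questionnaire #2 is then issued, and envelope #2 is sealed and collected at the end.
2. In Appendix D, amend Step 2 so that the patient hands in sealed envelope #1, Step 3 so that envelope #2 is received only after that, and Step 5 so that only envelope #2 is returned at the end. Bring the closing text of questionnaire #1 into line.
3. In Section 3.5.3, which has the study number recorded on the questionnaire before the patient receives it, state that the number goes on both forms so that they can be paired.

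The cost is a few sentences and one brief extra hand-over during a task that is meant to be done in private. A coordinator or designee already receives the forms; the protocol does not say who gives them out, so sites need to name that person. A card the patient brings along would still be controlled only by the instruction not to consult it.

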3.3 Cognitive Pretesting

In order to thoroughly evaluate the physician and patient questionnaires in preparation for fielding the study, RTI Health Solutions (RTI-HS) conducted cognitive pretesting with physicians and patients in each country.

Cognitive pretest interviewing is a well-established qualitative research methodology used to identify problems with questionnaire items and response options (Groves et al., 2009). Specifically, trained interviewers asked pretest participants to complete the questionnaires while thinking aloud or describing their thought processes as they answer the questionnaire items. Pretest interviewers used an interview guide that included probe questions designed to help interviewers understand how each participant interpreted and chose his or her answers for each item in the draft questionnaires. The pretest interviews helped to identify problems with questionnaire items, wording, response choices, etc., and ensured that participants understand the questions. The pretest interview data were used to optimise the language used in the questionnaires prior to fielding the patient and physician assessments. Likewise, the cognitive testing helped to identify cultural or translational issues with the draft questionnaires so that they could be modified to meet the individual needs of each country while maintaining comparability across the study. The pretest interviews also provided an opportunity to test procedures and introductory materials in an effort to increase participation and thoughtful consideration of the questionnaires by participants during collection of the study data.

Cognitive pretesting of the physician questionnaire was conducted with 25 physicians across the five countries who prescribe rivaroxaban for SPAF or DVT treatment and secondary

prevention. Additionally, cognitive pretesting of the patient questionnaire was conducted with 25 patients across the five countries who were being treated for SPAF or DVT/PE. Changes to both questionnaires were made based on the results of the cognitive testing and additional feedback from the sponsor. In addition, the patient questionnaire will now include re-administration of selected questions to evaluate patients' understanding of key safety information following exposure to the patient alert card.

3.4 Adverse Event Reporting

This study is not designed to collect information on individual adverse drug events, which are better collected using other study designs. However, spontaneous adverse drug reactions (ADRs) may be identified through the following pathways:

- Communicated during the qualitative cognitive pretesting interviews
- Documented through open-ended responses (if applicable) in the Web questionnaire completed by the HCP
- Documented through open-ended questions (if applicable) or handwritten notes on the questionnaire completed by the patient

For the cognitive pretest interviews, the interviewers completed safety training, which included instructions to complete an ADR case report form and submit it to the BHC pharmacovigilance country head (PVCH) if a spontaneous ADR was reported.

For each assessment, questionnaire data will be reviewed for possible ADRs. Upon identification of an ADR, this information will be forwarded to the BHC PVCH within 1 business day by e-mail, fax, or other mechanism developed with BHC. BHC will assess the information for possible adverse events and product complaints and forward it for processing to the company safety database and/or to the Product Complaints group as applicable through BHC's usual reporting processes and standard operating procedures. The local contact to the PVCH will follow up with the patient's physician directly, if BHC determines that follow-up is needed and if the reporting patient has given consent for his/her physician to be contacted by BHC. All initial and follow-up information will be de-identified and reported to BHC.

If a patient spontaneously reports an ADR to a physician during their participation in the study at the site, physicians will be expected to report suspected ADRs to the applicable manufacturer/licensee and/or regulatory authority in accordance with local procedures.

3.5 Ethical and Scientific Aspects

3.5.1 Protection of Human Subjects

This study will be conducted in accordance with all applicable ethical and regulatory requirements, including, where applicable, the 1996 version of the Declaration of Helsinki. The institutional review board (IRB) at RTI International (of which RTI-HS is a division) will review the study protocol, questionnaires, and informed consent documents. IRB/ethics committee (EC) approvals will be obtained in accordance with applicable national and local regulations in each country.

3.5.2 Ethical, Regulatory, and Scientific Principles

This study is being conducted as a regulatory commitment. As an observational study, the risks for patients linked to their participation in the study are limited to a breach of confidentiality with regard to personal identifiers or health information. Before a patient can participate in the study, he or she must give informed consent. Independent EC approval will be according to the guidance of the each country's research ethics requirements.

The study will be conducted under the following guidelines:

- The International Society for Pharmacoepidemiology 2008 *Guidelines for Good Pharmacoepidemiology Practices (GPP)* (http://www.pharmacoepi.org/resources/guidelines_08027.cfm)
- The Council for International Organizations of Medical Sciences (CIOMS) 2009 *International Ethical Guidelines for Epidemiological Studies* (http://www.cioms.ch/frame_ethical_guidelines_2009.htm)
- CIOMS 2002 *International Ethical Guidelines for Biomedical Research Involving Human Subjects* (www.fhi.org/training/fr/retc/pdf_files/cioms.pdf)
- The study will be designed in line with the European Network of Centres for Pharmacoepidemiology and Pharmacovigilance (ENCePP) *Guide on Methodological Standards in Pharmacoepidemiology* (ENCePP, 2012).
- The study will be reported according to the STROBE (Strengthening the Reporting of Observational Studies in Epidemiology) *checklist* (<http://www.strobe-statement.org/index.php?id=available-checklists>).
- This study will comply with the European Medicines Agency (EMA)'s *Guideline on Good Pharmacovigilance Practices (GVP). Module VI – Management and reporting of adverse reactions to medicinal products* (EMA, 2012b).

- The study will comply with the definition of a non-interventional (observational) study provided in the EMA's *Guideline on Good Pharmacovigilance Practices (GVP): Module VIII – Post-Authorisation Safety Studies* (EMA, 2012a).

3.5.3 Informed Consent

Participant informed consent will be obtained for each patient or physician who agrees to complete a questionnaire. Patient informed consent will be obtained in writing in all participating countries. Physicians will be asked to provide electronic acknowledgement of consent prior to completing the Web-based questionnaire.

The questionnaires will not collect any identifying information about the patient or physician, and they will be tracked using a unique study identifying number. For paper questionnaires, the physician will record the patient's study number on the questionnaire before it is given to the patient. Physicians will be required to provide limited data on each participating patient (e.g., diagnosis, surgeries, and treatment duration).

3.5.4 Participant Confidentiality

The research team will not have access to any participant-identifying information. No personal identifying information will be removed from the centres. Only de-identified data will be made available to the research staff and BHC. Thus, any reports that are generated will *not* contain any participant identifiers. Data will be provided to BHC in aggregate only and will not be linked to individual patients or HCPs.

For the patient assessment, sites will maintain an enrolment log with only the names of patients who completed the study and HCPs involved in the study. Site logs will be maintained at the site and will never be shared with the research team, third parties, or BHC. Additionally, the patient questionnaire will *not* be linked to any patient log or any other patient-identifying information. Additionally, age in lieu of a birth date will be used to further protect confidentiality.

3.5.5 Compensation

Physician sites participating in the patient assessment will be paid nominal incentives to compensate them for the time spent recruiting patients and providing limited data from patient records, per country-specific regulations. The amount and payment methods will be reviewed and approved by the IRB/EC to ensure that payments are commensurate with the time needed to complete the study tasks and are not coercive.

Patients and physicians participating in the assessments will be paid nominal incentives to compensate them for their time in completing the study questionnaires in those countries where it is acceptable to do so. As with the site compensation, the amount and payment methods will be reviewed and approved by the IRB/EC to ensure that payments are commensurate with the time needed to complete the forms, not coercive, and made according to local regulations in each country.

3.6 Data Management

A data management plan will be developed to guide the handling of data, including the transfer of electronic files. The data management plan will include, if necessary, country-specific modifications due to local regulations or requirements. Physician data will be entered directly into a Web-based EDC system. Patients will fill out data on paper forms, which will be sent to a data processing centre for double data entry that will be used to minimise data entry errors. Edit and logic checks will be conducted and queries resolved to ensure high-quality data. However, due to the self-reported nature of the data some such resolutions may not be possible.

RTI-HS data managers will conduct user acceptance testing (UAT) and will sign the UAT report before the EDC system is used in the field. Staff will be trained on data collection forms and the EDC system before the study is fielded. RTI-HS data managers will approve the data management plan, all annotated data collection forms, the EDC and double-data entry system data dictionaries, the data cleaning specifications document, and the testing summary reports before authorizing the data systems to go "live." RTI-HS data managers will ensure that the EDC and paper data systems are tested and valid, and will require that testing documentation, database documentation, and change control documentation will be created and maintained.

Once the systems are in the field, data management activities will include review of interim analysis files for consistency, programming edit checks in preparation for statistical analysis, and merging datasets if required.

